Clinical Trials Study Protocol

Examining Transcutaneous Vagal Nerve Stimulation as a Facilitator of Social Bonding (NCT05899413)

Version 1

March 1, 2025

This study was approved by the Institutional Review Board at the University of California, San Francisco (#23-39189). We conducted a power analysis prior to the data collection to determine the power for the Level-2 direct effect (stimulation condition) based on 1,000 simulations using the package *simr* in R (R Core Team). Given the nature of our dyad and the outcomes (i.e., questions about the same interaction), we assumed a large intraclass coefficient (0.5). Following Arend and Schäfer's (2019) recommendations, the standardized Level-1 direct effect was set to small ($\gamma_{std.} = .10$) in our power estimation for the Level-2 effect. Our analysis suggested that 70 dyads will provide > 82% power (α set to .05) to detect a medium-to-large standardized Level-2 direct effect ($\gamma_{std.} = .40$).

Data collection for the study took place between February and June 2024. Participants were recruited in the San Francisco Bay Area through various community and university newsletters and listservs, flyers around the city, Reddit, and word of mouth. We tried to reach diverse populations by promoting the study through various community centers (e.g., SF LGBT Center) and universities in the city (e.g., San Francisco State University, UC Berkeley).

Eligibility was confirmed using a screening questionnaire. Participants were eligible for the study if both they and their partner were between 18 and 35 years old, fluent in English, had no major chronic diseases (e.g., cardiovascular disease) or untreated psychiatric diagnoses, were not taking any confounding medications (e.g., antihypertensive medications), and did not have unremovable piercings on the tragus. We restricted the age range to control for age-related differences in physiological responses. As HRV tends to decrease with age, we attempted to recruit a more homogenous group on one of our primary outcome variables (HRV level and reactivity), so we capped the age range to mid-adulthood. Participants were also required to have been in a relationship with their partner for at least one year and be able to complete the inperson laboratory visit together.

Tasks and Measures

Pre-visit survey. Prior to the lab visit, participants completed pre-visit surveys that collected information on basic sociodemographic characteristics, relationship characteristics, and physical attributes, including height and weight. Self-reported height and weight were used to compute Body Mass Index (BMI; weight (*lb*) ÷ height² (inches) * 703), which we used as a covariate. Participants also responded to a 5-item measure of relationship satisfaction (e.g., "I feel satisfied with our relationship"; $\alpha = .81$) and a 7-item measure of commitment (e.g., "I want our relationship to last for a very long time"; $\alpha = .79$) from the Investment Model Scale (Rusbult et al., 1988), which we used to test differences between participants in the experimental and control conditions. Additionally, they rated 24 relationship issues (e.g., communication, family and in-laws; adapted from Geiss & O'Leary, 1981) on a scale ranging from 0 (*issues that rarely if ever raise conflict or disagreement*) to 10 (*issues that raise frequent or intense conflict or disagreement*). Participants' responses to this scale were used in the conflict interaction described below.

Gratitude interaction. The procedures were based on Algoe and colleagues (2013). Couples were told to think about a positive thing their partner did for them recently for which they felt grateful. They were given three minutes to prepare, then took turns to express their gratitude for three minutes each. While one partner was speaking, the listening partner was told to listen with minimal verbal reactions.

Conflict interaction. The procedures were based on Levenson and Gottman (1983) and previous studies that examined physiological reactivity during conflicts (e.g., Godfrey & Babcock, 2020; Raby et al., 2015). Couples were told that they would discuss a conflict topic

relevant to their relationship and try to resolve it. The interaction would involve the following steps: 1) couples selecting a topic to discuss together, 2) reflecting on the topic independently for three minutes, 3) each partner taking turns expressing their thoughts and feelings about the topic for one minute (the speaking order was predetermined based on the alphabetical order of their first names), and 4) couples engaging in free discussion for six minutes, with the goal of resolving the issue.

After receiving the instructions, couples were given a list of three topics to choose from. Unknown to the couples, this list was generated using participants' responses regarding the frequent topics of arguments that they provided in the pre-visit survey. The three topics were chosen based on the highest average ratings of the two partners. If no topics averaged higher than 3, the list included an option of "any topic that recently triggered a conflict or disagreement in the relationship."

Following the interaction, participants completed a short questionnaire that included measures of **positive affect** ("During the conversation, overall, I felt..."; 1: not at all positive, 7: extremely positive) and **negative affect** ("During the conversation, overall, I felt..."; 1: not at all negative, 7: extremely negative).

tVNS device and stimulation. We used a research edition of an auricular vagus nerve stimulator (tVNS RE, Vagus.net[™], UK) that sends current-controlled stimulation in symmetric biphasic waveforms. The tVNS RE conforms to EU directive 93/42/EEC medical device standards and ISO/IEC 17050-1. This device consists of a handheld stimulator and an electrode clip. Following previous research (Kraus et al., 2007), couples in the sham stimulation condition had the electrode clip placed on the center of their left earlobe (free of cutaneous vagal innervation; Peuker & Filler, 2002) while those in the tVNS condition had the electrodes placed on their tragus. While cymba concha has also been used for tVNS, there is no evidence that psychophysiological effects of tVNS depend on the stimulation site (Borges et al., 2021). In fact, tVNS effects on executive functioning may be larger when stimulation is applied at the tragus rather than cymba concha (Ridgewell et al., 2021). We stimulated the left ear, which has been a common practice as the efferent vagal fibers to the heart are located on the right side (Kim et al., 2022) but note that the side effects are considered negligible and studies have also used rightsided stimulation (see Kaduk et al., 2023).

The experimenter first cleaned the stimulation loci with alcohol cotton swabs to reduce skin resistance. To identify the lowest stimulation intensity that participants could perceive, we adopted the staircase procedures used in previous research (e.g., Schuerman et al., 2021). Specifically, the experimenter placed the electrode clip on the participant's left ear (tragus or earlobe) and increased the stimulation levels by 0.1 mA, starting from zero, until the participant reported feeling a tingling sensation. Experimenters confirmed the threshold twice, and the stimulation level was set 0.2 mA below each participant's perceptual threshold (Schuerman et al., 2021) to allow couples to converse as naturally as possible and to attempt to keep participants unaware of their condition assignment. We delivered stimulation at the individually calibrated intensity continuously during the interaction, and the default device settings we adopted were as follows: frequency = 30 Hz, phase duration = 250μ s, interphase interval = 50μ s, and max voltage = 65 V.

Physiological data acquisition. Participants' physiological responses were continuously recorded during the baseline and all interactions. We collected electrocardiography (ECG) and impedance cardiography, which were integrated using an MP150 system (Biopac Systems Inc., Goleta, CA). Spot sensors were placed in a modified lead II configuration on the torso (near the

right clavicle and below the left rib cage) to measure ECG (Mendes, 2009). Data were acquired using Acqknowledge software at a sampling rate of 1000Hz (Biopac Systems Inc, Goleta, CA, USA). RSA was edited and scored in 30-second intervals using the HRV module from Mindware Technologies (Gahanna, OH), which identified the R spikes of each heartbeat in the ECG. Although 60-second epochs are generally recommended, 30-second epochs have been reliably used in previous dyadic studies (Caldwell et al., 2018; Oshri et al., 2023; Qaiser et al., 2023) and may sufficiently capture high-frequency activity especially when the heart rate is elevated (i.e., shorter heart period; Quigley et al., 2024), as in conflict settings. After data collection, trained research assistants blind to the condition visually inspected all data for artifacts and edited them as needed (e.g., removal of misplaced R-peaks).

Post-study survey. At the end of the study, before debriefing and being informed of the condition they were assigned to, participants answered a few questions about their experience of the stimulation and the tVNS device. Specifically, we asked about **awareness of the stimulation** ("How much, if at all, could you feel the tingling sensation during the conversations?"), **general discomfort** ("How uncomfortable was wearing the tVNS device [i.e., the clip you had on your ear] throughout the study?"), **perceived influence of discomfort on interactions** ("How much, if at all, did the discomfort [from wearing the clip] affect your conversations?"), and **perceived influence of tVNS on interactions** ("How much, if at all, do you think the device changed the way you felt or interacted with your partner during the conversations?"). All items were rated on a 5-point scale.

Study Procedure

Interested participants first completed a screening questionnaire to confirm eligibility. Eligible participants were then contacted via email to schedule a lab visit. Two days prior to the scheduled visit, participating couples received a link to a consent form and a questionnaire assessing sociodemographic information and relationship characteristics. Couples were randomly assigned to either tVNS or sham stimulation condition when they both completed the pre-visit survey. Each couple had an equal chance of being in either group.

Upon arrival at the lab, partners were escorted to separate rooms where they each received a full overview of the study and underwent threshold testing for stimulation. Then partners reunited in the same room, were connected to physiological sensors, and spent five minutes, resting in a comfortable seated position (baseline). As shown in Figure 1, they were seated at an angle, partially facing each other, with their bodies slightly tilted toward the front where a fixed wall-mounted camera was positioned. Participants were recorded during gratitude and conflict interactions. Full study procedure, including the timing of the stimulation is illustrated in Figure 2. Following a cool-down period, participants completed a brief questionnaire about their experience with the stimulation and were debriefed. They also signed an additional consent form for the use of their recorded videos.

Figure 1. Example Positioning of the Couple During the Study

[figure not shown]

Figure 2. Overview of Study Procedure

Notes. The time next to the lightning icon indicates the duration of the (active or sham) stimulation. The time at the bottom represents the duration of each study segment described within the rectangles. The survey icon indicates when participants complete short questionnaires.

Statistical Analysis Plan

All analyses will be conducted in R (R Core Team, 2022). Multilevel model analyses will be conducted using the packages *nlme* and *lmer*. All tests will be two-tailed, with a significance threshold of $\alpha = .05$.

Randomization check. We will first examine whether there are condition differences in personal and relational characteristics at baseline, including age, relationship duration, global relationship satisfaction, and commitment. To account for the interdependence of the dyadic data, we will fit a series of multilevel models with a random intercept included for participants nested within couples and condition included as a fixed effect. Restricted Maximum Likelihood will be used to fit the model parameters. For relationship duration, which is a couple-level variable, Welch's t-test will be conducted. **Study artifact check.** We will examine if there are condition differences in participants' experiences related to the stimulation and the tVNS device reported at the end of the study, including awareness of the stimulation, general discomfort, perceived influence of discomfort on interactions, and perceived influence of tVNS on interactions. We will run a parallel set of multilevel models as described above.

tVNS effects on emotional experience of the conflict. We will examine if there are condition differences in how couples self-report their experience of the conflict interaction, specifically in terms of positive and negative affect during the interaction. We will run a parallel set of multilevel models as described above.

tVNS effects on physiological reactivity. As in previous research, we will calculate reactivity scores by subtracting the raw RSA score during the last 30 seconds of baseline from every segment of the interaction. We will fit a multilevel model, first estimating the effect of condition (coded as -0.5 for sham and 0.5 for tVNS) on RSA reactivity with no covariates. As in previously described multilevel models, we will include a random intercept for participants nested within couples, and as recommended for physiological data, with autoregressive covariance structure of the residuals. In our follow-up models, we will control for sex (male/female/other), age, BMI, and relationship duration, which can influence physiological reactivity to conflicts. Then, to rule out the possibility that any condition effects are reducible to differences in the experience of the stimulation, the next model will additionally control for stimulation intensity and discomfort reported at the end of the study. We will repeat these analyses using IBI in place of RSA.

References

- Algoe, S. B., Fredrickson, B. L., & Gable, S. L. (2013). The social functions of the emotion of gratitude via expression. *Emotion*, 13(4), 605–609.
- Arend, M. G., & Schäfer, T. (2019). Statistical power in two-level models: A tutorial based on Monte Carlo simulation. *Psychological Methods*, 24(1), 1-19.
- Caldwell, W., da Estrela, C., MacNeil, S., & Gouin, J. P. (2019). Association between romantic partners' rumination and couples' conflict is moderated by respiratory sinus arrhythmia. *Journal of Family Psychology*, 33(6), 640-648.
- Geiss, S. K., & O'Leary, K. D. (1981). Therapist ratings of frequency and severity of marital problems: Implications for research. *Journal of Marital and Family Therapy*, 7(4), 515-520.
- Godfrey, D. A., & Babcock, J. C. (2020). Facial affect recognition moderates the relation between autonomic nervous system reactivity and aggression during dyadic conflict. *Psychophysiology*, 57(9), e13588.

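### Does the single power figure, with an undefined effect scale and an ICC argued from questionnaire items, leave the HRV analysis without a sound basis?

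*Combined protocol and SAP*

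**What the plan says.** The power paragraph in the opening section reports 1,000 simulations in simr for the Level-2 effect of stimulation condition: "Our analysis suggested that 70 dyads will provide > 82% power (α set to .05) to detect a medium-to-large standardized Level-2 direct effect" of .40, with a Level-1 effect of .10. On clustering it says: "Given the nature of our dyad and the outcomes (i.e., questions about the same interaction), we assumed a large intraclass coefficient (0.5". It names no outcome for the power result itself. It does not say which SD standardizes .40 or how condition was scaled in the simulation.

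The eligibility paragraph of the same section calls HRV "one of our primary outcome variables (HRV level and reactivity".

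The physiological data have a further level. Under Physiological data acquisition, "RSA was edited and scored in 30-second intervals". Under Conflict interaction, the last step is "couples engaging in free discussion for six minutes", after two one-minute turns.

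The Statistical Analysis Plan opens with "All tests will be two-tailed, with a significance threshold of" .05. Its subsection on physiological reactivity codes condition -0.5 for sham and 0.5 for tVNS. It continues "we will include a random intercept for participants nested within couples, and as recommended for physiological data, with autoregressive covariance structure of the residuals", and after the covariate models it adds "We will repeat these analyses using IBI in place of RSA". Neither the power paragraph nor the SAP gives a power figure, an SD or a detectable difference specific to RSA or IBI. The SAP does not mention confidence intervals.

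**The concern.** Three things look wrong together.

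- **Scale.** A standardized effect means little until the SD is named. The SAP's -0.5/0.5 coding makes the condition coefficient a difference in means. A reader who takes .40 as a 0.40 total-SD difference at ICC 0.5 gets about 48% power, not 82%.
- **Outcome.** The ICC is argued from partners answering questions about a shared conversation. That argument does not carry over to ECG-derived RSA, which is analysed in repeated segments with autoregressive residuals, whereas the power calculation has two levels.
- **Interpretation.** With a .05 threshold and no stated interval, a non-significant RSA result might be read against the 82% figure, which may not apply to it.

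If all this held with consequences, the trial could be badly underpowered for a primary outcome and unable to say which tVNS-sham differences its data exclude.

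**Working it through.** **Inputs.** From the documents: 70 couples, equal chance of either arm, two-sided .05, ICC 0.5, Level-2 effect .40, Level-1 effect .10. Assumed: exactly 35 couples per arm, no missing data, and a partner correlation r for RSA of 0 to 0.5.

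**1. Reproducing the stated power.** Read .40 as a slope per SD of condition, in units of the between-couple SD. Set the between-couple and within-couple variances to 1 each (ICC 0.5).

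- Between-couple variance left after condition: 1 - .40² = .84
- Within-couple variance left after the Level-1 effect: 1 - .10² = .99, or .495 for a couple mean
- SE of slope = sqrt((.84 + .495)/70) = .138
- .40/.138 = 2.90
- Power = 82.5% (normal) or 81.5% (noncentral t, 68 df)

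This is close to the stated figure, and 1,000 simulation runs carry an error of about sqrt(.82 × .18/1000) = 1.2 percentage points. The implied arm difference is .40/.5 = .80 between-couple SD. That is .80/sqrt(2) = .57 total SD, or .80/sqrt(.84 + .99) = .59 within-arm SD.

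The scale is inferred. Other readings of .40 give anything from about 27% to 99%: for example 48% by t if it is a total-SD difference, and 97% if it is a slope per SD of condition in total-SD units. Only the sponsor can confirm which was used.

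**2. What the ICC does to power for RSA.** Work in within-arm SDs of a person's mean reactivity. A couple mean has variance (1 + r)/2, so

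SE of arm difference = sqrt(4 × ((1 + r)/2)/70)

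Power and detectable difference are by noncentral t with 68 df. The 95% half-width is 1.995 × SE.

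| r | SE | Power for 0.59 SD | Detectable difference, 80% power | 95% half-width |
|---|---|---|---|---|
| 0 | .169 | 93% | 0.48 | 0.34 |
| 0.1 | .177 | 91% | 0.50 | 0.35 |
| 0.3 | .193 | 86% | 0.55 | 0.38 |
| 0.5 | .207 | 80% | 0.59 | 0.41 |

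A lower partner correlation raises power. Within this range the assumed 0.5 is the conservative end.

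**3. The segment level.** Six minutes in 30-second segments give 12 segments, or 16 with the two one-minute turns. In person-mean units the segment count is absorbed into the SD. Simulated three-level data with AR(1) residuals, tested on couple means at the difference targeted for 82% power, gave 80.6% to 83.5%. That is close to what the choice of units guarantees, so it only confirms that the extra level does no hidden damage on this scale.

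**4. What the planned model yields.** With condition coded -0.5 and 0.5, the coefficient is 0.5 - (-0.5) = 1 unit of condition, which is tVNS minus sham in RSA units. The mixed-model fit returns its standard error, and the 95% interval follows directly. The same holds for IBI.

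**The case for a change.** The strongest case for a change is that the fix is cheap. One sentence would define the scale of .40, and one would commit to a 95% interval. Readings of .40 span roughly 27% to 99% power, the label Level-2 hints at a scale without defining it, and the SAP is written in the future tense, so a reporting line could still be added. A partner correlation above 0.5 would also work against the trial: by the same formula, power for 0.59 SD falls to 75% at 0.7 and 73% at 0.8.

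Some of this stands. The power paragraph is incompletely documented, and power for RSA and IBI is not established in the documents. But nothing shows it to be below 82%, and nothing in the documents suggests that partners' RSA reactivity correlates above 0.5. Text limiting the 82% to self-report outcomes would go beyond the source, which ties only the ICC to questions and names no outcome for the power. Writing in 0.80 between-couple SD would turn an inference into a statement of what the sponsor did. A detectable difference in person-mean SDs could not be read in RSA units, since no RSA SD is given. The interval is a routine product of a model that is already specified.

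**Conclusion.** The concern is accurate as description but calls for no change: this is missing detail that competent analysts fill in the ordinary way. The > 82% is not an arithmetic error. It approximately reproduces on one plausible scale, at about 0.57 total SD (0.59 within-arm SD). For RSA and IBI, over partner correlations of 0 to 0.5, power for a 0.59 SD difference is 93% down to 80%, so borrowing 0.5 from the questionnaire argument does not flatter the design.

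The planned coefficient is already the treatment difference. Its interval, with expected half-width 0.34 to 0.41 SD, shows what a non-significant result can exclude, without reference to the 82%. With recruitment finished in June 2024, rewriting the power paragraph would alter no estimate, test or sample size.

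This rests on 35 couples per arm, complete data, and a partner correlation for RSA no higher than 0.5. It also rests on the inferred scale for .40, which only the sponsor can confirm.

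### HRV level, named as part of a primary outcome, has no planned analysis, and the post-calibration baseline behind the reactivity score is neither adjusted for nor compared between arms

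*Combined protocol and SAP*

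**What the plan says.** **Outcome.** The eligibility paragraph at the start of the protocol explains the age cap by reference to "one of our primary outcome variables (HRV level and reactivity". It is the only place where the documents call any outcome primary; there is no formal outcome list.

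**Analysis.** In the SAP, under tVNS effects on physiological reactivity: "we will calculate reactivity scores by subtracting the raw RSA score during the last 30 seconds of baseline from every segment of the interaction". The first model estimates the condition effect "on RSA reactivity with no covariates". Later models add sex, age, BMI and relationship duration, then stimulation intensity and discomfort. The section ends: "We will repeat these analyses using IBI in place of RSA".

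**Baseline comparison.** The Randomization check looks at personal and relational characteristics, "including age, relationship duration, global relationship satisfaction, and commitment". Baseline RSA is not named.

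**Sequence.** Under Study Procedure: "Couples were randomly assigned to either tVNS or sham stimulation condition when they both completed the pre-visit survey". At the visit, partners "underwent threshold testing for stimulation" before sensors were attached and the five-minute rest began. Under tVNS device and stimulation, that testing is done at the tragus or the earlobe according to arm. Current rises from zero in 0.1 mA steps until it is felt, the threshold is confirmed twice, and the study level is then set 0.2 mA lower.

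**The concern.** The protocol treats level and reactivity as two components of a primary outcome. The SAP analyses one of them. If the plan is followed exactly, HRV level gets no estimate and no test, and a reader cannot tell whether it was dropped on purpose.

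The component that is analysed subtracts one 30-second baseline value. That value is recorded after randomisation and after current was applied at an arm-specific site, briefly reaching a higher intensity than the study stimulation. Because sensors were attached only afterwards, the described procedure yields no RSA from before calibration. The plan has no step that would show whether the arms already differed at that point.

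**Working it through.** **1. Which models exist.** RSA is taken here as the HRV measure, since the protocol scores it with an HRV module.

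| Quantity | Planned analysis |
|---|---|
| RSA change from baseline | Yes, three models |
| IBI change from baseline | Yes, same sequence |
| RSA level during the interaction | None |
| Baseline RSA by arm | Not named |
| Baseline RSA as covariate | Not named |

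**2. The plan's own power figure, used below only as a scale.** Take 70 dyads as 35 per arm, ICC 0.5, and .40 as a fully standardised couple-level coefficient with ±1 coding. The arm difference is 2 × 0.40 = 0.80. The couple-mean SD is √[(1 − 0.4²) + (1 − 0.1²)/2] = √(0.84 + 0.495) = 1.155. The standard error is 1.155 × √(2/35) = 0.276, so power is Φ(0.80/0.276 − 1.96) = 82.5%, which agrees with the stated figure of more than 82%. Read as a plain difference of 0.40 total SDs, power would be 48.9%. The present point does not depend on which reading is right.

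**3. What a calibration shift would do.** Let d be the true effect during the interaction, s the arm difference in baseline RSA caused by calibration, and k the share of s still present during the interaction. The documents give neither s nor k.

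- Unadjusted level contrast: d + ks
- Change-score contrast: d + ks − s = d − (1 − k)s
- Level adjusted for baseline, equal variances, baseline correlation r: about d + ks − rs = d + (k − r)s

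At k = 1 the shift vanishes from the change score. At k < 1 it enters with the opposite sign, up to −s. The adjusted model removes r times the shift: half at r = 0.5, 70% at r = 0.7.

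Illustration for the change score on the scale of step 2, with assumed positive s and the SD held at 1.155:

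| s | k | Contrast (d = 0.80) | Power | Rejection rate when d = 0 |
|---|---|---|---|---|
| any | 1 | 0.80 | 82.5% | 5.0% |
| 0.2 | 0.5 | 0.70 | 71.7% | 6.5% |
| 0.2 | 0 | 0.60 | 58.4% | 11.2% |
| 0.4 | 0 | 0.40 | 30.4% | 30.5% |

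A negative s would inflate the contrast instead.

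**4. Precision.** For one baseline and one follow-up value with equal variances, the variance relative to unadjusted level (1.00) is 2(1 − r) for change and 1 − r² for baseline-adjusted level. Their ratio is (1 − r²)/[2(1 − r)] = (1 + r)/2. The documents do not give r.

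| r (assumed) | Unadjusted level | Change | Adjusted level | Adjusted ÷ change |
|---|---|---|---|---|
| 0.3 | 1.00 | 1.40 | 0.91 | 0.65 |
| 0.5 | 1.00 | 1.00 | 0.75 | 0.75 |
| 0.7 | 1.00 | 0.60 | 0.51 | 0.85 |
| 0.9 | 1.00 | 0.20 | 0.19 | 0.95 |

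The adjusted model is the more precise at every r below 1. The unadjusted level contrast is less precise than the change score once r exceeds 0.5; at r = 0.7 its variance is 1.00/0.60 = 1.67 times as large.

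**5. Testing both components.** Two independent tests at .05 give a familywise error of 1 − 0.95² = 9.75%, and less if they are correlated. At .025 each, the power in step 2 falls from 82.5% to 74.4%.

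**The case against.** The primary-outcome wording is a parenthesis in the reasons for an age limit, not an outcome definition. A reader might infer that a primary outcome goes wholly unanalysed. The documents do not support that: reactivity, the other component, has a full sequence of models, and the affect outcomes are tested without any baseline. Only the level component lacks a result.

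A reader might also infer that calibration contaminated the baseline and that the change score subtracts the effect out. Nothing in the documents shows a shift. The early steps of the staircase lie below perception. Sensor attachment and a five-minute rest follow, and only the end of that rest is used. Subtraction removes a shift completely only if it persists in full. These objections stand, so the calibration issue is a possibility to check and not a demonstrated bias.

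Change scores are also a common choice, and the SAP appeals to earlier research for them. The formula (1 + r)/2 is for one pre and one post value, whereas this design has many segments, clustering within couples and autoregressive residuals. The figures in step 4 are therefore indicative only. Finally, baseline adjustment uses the same post-calibration value, so it cannot by itself cure a calibration effect. All of this is accepted. It leaves untouched the mismatch between the protocol and the SAP and the absence of any look at baseline RSA by arm.

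**Conclusion.** The point holds in a limited form. The level component of the only outcome called primary has no planned analysis, and the baseline behind the reactivity score is post-randomisation, post-calibration, unadjusted for and not listed for comparison between arms. This follows from the text without assumptions, except that the Randomization check introduces its variables as examples, so a baseline RSA comparison is unnamed but not excluded.

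The size of any calibration bias is unknown, since s and k are assumptions throughout; it is nil if s = 0 or k = 1. The gain in precision from baseline adjustment rests on equal variances, an assumed r and the one-pre/one-post simplification: 25% lower variance than the change score at r = 0.5 and 15% at r = 0.7. Stimulation timing is taken from the text, as the procedure figure is not shown.

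**What to change.** In the SAP section on physiological reactivity:

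- Add a model with raw segment RSA as outcome, condition as the effect and baseline RSA as covariate, keeping the same random effects and autoregressive residuals.
- Report baseline RSA by arm alongside the Randomization check.
- Give the unadjusted level contrast as a sensitivity analysis. State that it is less precise than the change score when r exceeds 0.5, and that baseline adjustment alone does not remove a calibration effect.
- Name either level or reactivity as the single primary test, and make the eligibility paragraph agree. No split of alpha is then needed.
- Label the added models as specified after data collection, which ran from February to June 2024; this version is dated March 1, 2025.

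The cost is a few lines of text, one or two more model fits on data already recorded, and one more test to place in the testing order. Sample size is unaffected.

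### Should the affect tests adjust for relationship satisfaction and issue ratings collected before randomisation?

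*Combined protocol and SAP*

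**What the plan says.** The paragraph of the Statistical Analysis Plan on emotional experience of the conflict reads "We will examine if there are condition differences in how couples self-report their experience of the conflict interaction", naming positive and negative affect. For the model it says only "We will run a parallel set of multilevel models as described above". The template is the one under Randomization check: a random intercept for the dyadic structure and condition as the fixed effect, fitted by REML. No covariate is named, and no adjusted affect model appears elsewhere.

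The two candidate covariates come from the Pre-visit survey section. Satisfaction (5 items) and commitment (7 items) are described as measures "which we used to test differences between participants in the experimental and control conditions". The 24 issue ratings (0 to 10) serve to build the conflict topic list: "The three topics were chosen based on the highest average ratings of the two partners". Study Procedure states that a couple was randomised once both partners had finished this survey.

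For RSA and IBI, by contrast, the plan fits a condition-only model first. Follow-up models then adjust for sex, age, BMI and relationship duration, chosen because they may affect physiological reactivity.

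**The concern.** The worry has a sound statistical basis. Whole couples are randomised, so the precision of the condition estimate depends on the variance of couple means. A baseline variable that explains part of that variance narrows the interval. Satisfaction with the relationship and the intensity of its conflicts are natural candidates for predicting how a conflict discussion feels. Both were measured before allocation, so stimulation cannot have influenced them. The plan already reports adjusted models beside unadjusted ones for RSA and IBI. Leaving affect unadjusted can therefore look like an oversight that costs precision at 70 couples.

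Only precision would be at stake. Randomisation protects the condition-only estimate from bias, and its standard error already allows for chance imbalance in satisfaction or conflict level.

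**Working it through.** **Inputs from the documents.** 70 dyads; stated power above 82%; standardised Level-2 effect 0.40; Level-1 effect 0.10; ICC 0.5 (opening power paragraph). Two-sided alpha .05 (Statistical Analysis Plan). Equal chance of either arm (Study Procedure), taken here as 35 and 35 couples. **Assumed:** the share R² of within-arm couple-mean variance that the covariates explain. The documents give no figure, so 0 to 30% is shown.

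**The plan's own figure.** With two partners per couple, the condition test is a test on 70 couple means with variance τ² + σ²/2. Code condition ±1 and take each level's variance as 1 less its explained part: τ² = 1 − 0.40² = 0.84 and σ² = 1 − 0.10² = 0.99. Couple-mean variance is 0.84 + 0.495 = 1.335. The arms differ by 0.8, with SE √(1.335 × 2/35) = 0.276, so the ratio is 2.90. Power is 82.5% (normal) or 81.5% (t, 68 df), in line with the plan. This standardisation is assumed; other readings of 0.40 give 28% to 49%, 78% or 97%. The width ratios below do not depend on it.

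**Effect of adjustment.** For k couple-level covariates,

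width ratio = √[(1 − R²)(1 + k/(70 − k − 3))] × t(.975, 68 − k)/t(.975, 68).

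With k = 2 (satisfaction and one issue score) the second factor is 1 + 2/65 = 1.0308 and the t ratio is 1.0005. At R² = 10%: √(0.90 × 1.0308) × 1.0005 = 0.964.

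| R² | Interval width, adjusted ÷ planned | Adjusted interval narrower (share of simulated trials) | Equivalent couples, 70/[(1 − R²) × 1.0308] |
|---|---|---|---|
| 0% | 1.016 | 18% | 68 |
| 5% | 0.990 | 57% | 71 |
| 10% | 0.964 | 81% | 75 |
| 20% | 0.909 | 97% | 85 |
| 30% | 0.850 | over 99% | 97 |

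Break-even is R² ≈ 3%. At ICC 0.5 the between-couple share of couple-mean variance is 0.5/0.75, so R² = 10% means explaining 0.10 × 0.75/0.5 = 15% of true between-couple variance.

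**Size on the affect scale.** In units of the individual SD, couple-mean variance at ICC 0.5 is 0.75. The 95% half-width is therefore 1.996 × √(0.75 × 2/35) = 0.41 SD. Affect is a single 1–7 item. For an assumed SD of 1 to 2 points, R² = 10% trims 0.036 × 0.41 SD ≈ 0.015 to 0.03 points from each side. R² = 30% trims 0.15 × 0.41 SD ≈ 0.06 to 0.12 points.

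**Dependence on covariate form.** With four covariates the break-even rises to 6.2%, and the gain at R² = 10% falls to 2.1%. Entering all 24 issue ratings plus two others (k = 26) would widen the interval by 23% at R² = 10%.

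**Error rate.** In 40,000 simulated null trials per R² value, each model alone rejects in 4.8% to 5.1%. If either could be claimed, at least one rejects in 5.6%, 6.2%, 6.4%, 7.0% and 7.4% at the five R² values. The plan has one model per affect outcome, so this inflation is absent from it; only a second model could introduce it.

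**The case for a change.** The strongest case for adjustment is that the data are in hand, they precede randomisation, and few couples should lack them. The cost of useless covariates is bounded at 1.6% of interval width. At R² of 20% to 30% the gain would match having 85 to 97 couples instead of 70. If the condition-only model were fixed as the deciding test, the error rate would stay at 5%.

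The facts and the conditional arithmetic stand. An adjusted affect model would have been a legitimate choice had it been named beforehand. Three things keep it from being a fault that it was not.

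- Nothing in the documents places R² at 10% or more rather than below 3%. An issue score averaged over a couple's top three topics may predict poorly: "After receiving the instructions, couples were given a list of three topics to choose from", and they discuss only one. Where no topic averaged above 3, they could also choose an unrated topic of their own.
- If the condition-only model decides, as it must to hold the error rate, the adjusted row changes neither the planned test's power nor its result. Power of 84% to 92% at R² of 10% to 30% would apply only if the adjusted model replaced the planned test.
- The timing is unfavourable. The plan says "Data collection for the study took place between February and June 2024", and this version is dated March 1, 2025. Choosing satisfaction over commitment, couple means, and a new three-issue score would all be decisions taken after collection.

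The RSA and IBI models do not make the affect plan inconsistent. Their covariates were chosen for physiological reasons, and neither satisfaction nor issue ratings is among them.

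**Conclusion.** The concern does not hold. The condition-only affect test is a valid, unbiased comparison of randomised couples, and no other part of the plan contradicts it. Adding satisfaction and one issue score would change the interval width by between +1.6% and −15% over an assumed R² of 0 to 30%. At 10% the interval is 3.6% narrower on average and still wider in about one trial in five. These figures rest on 70 couples split evenly and two couple-level covariates; the documents do not state the number analysed. Reasonable statisticians could add such a model as a supplement or decline it. Its absence biases nothing and changes no planned conclusion.
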